### 5.1.5. Explanatory Variables (Covariates) Description

Covariates will include:

- Demographic characteristics (e.g. age, race, gender)
- Clinical characteristics (e.g. Charlson comorbidity index score)
- Past medical services utilization
- Insurance type
- English as second language
- Type of care management program received (programmatic subgroup)
- Discharge location characteristics
- Community characteristics (e.g. % under federal poverty level)

### 5.2. MVP Program - Intervention Description

Population Health's Multiple Visit Patient (MVP) care management program aims to manage health and lower hospital utilization among patients with a history of high inpatient hospital stays at Atrium Health. Patients eligible for the program have four or more inpatient visits over the 12-month period prior to enrollment. Once enrolled, each MVP program participant receives on-going support from an assigned MVP care manager and larger care management team, including the following core program components:

- customized care plan developed for each patient at the time of enrollment
- routine, virtual health monitoring and collaborative care management team-based review
- personalized navigation and coordination across multidisciplinary Atrium Health services, as needed
- education, health coaching, and support via telephonic and in-person interactions, as needed

**Screening and care manager assignment.** A list of patients with four or more inpatient hospital visits in 2019 will be pulled from the Atrium Health electronic data warehouse (EDW). The care management team will review eligibility for the MVP program. The list of eligible participants will be randomized using parallel block randomization approach into the 2020 MVP program cohort (intervention) and the control group.

Eligibility for the program is based on past utilization, with patients with 4 or more inpatient visits over a 12-month period qualifying for the program. To identify the new MVP cohort, the list of patients with highest volume of inpatient hospital visits is generated by Clinical Analytics. The care management leadership team then reviews the chart of each patient on the list to determine eligibility and assigns the patient to the appropriate care management group. The number of patients accepted to the MVP program is constrained by the care management group's capacity. Existing MVP enrollees continue to receive care from their currently assigned team. Patients are assigned to a distinct care management group based on insurance/care needs:

- i. Ambulatory Care Management (ACM)
  - Commercial insurance

- Medicare only
  - Medicare with Medicaid as second
  - Uninsured outside of Mecklenburg and Union counties
  - Non CA II Medicaid
- ii. Community Care Partners (CCP)
    - Medicaid CA II
      - a. Priority list (determined by the Medicaid state program)
      - b. Provider preferred
    - Community Care of NC (CCNC)
      - a. Medicaid CA II that are not being managed by CCP (ie Mecklenburg, Union, Anson counties)
- iii. Community Care Bridge (CCB)
    - Uninsured in Mecklenburg and Union counties
  - iv. Advanced Illness Management (AIM)
    - Patients with a limited prognosis but for whom hospice is not yet an option.  
This program is part of Continuing Care.

**Program Start Point.** Patients in the intervention group are enrolled in the MVP program at one time point determined by Care Management leadership. The start point is marked by an “Active” indicator in the Patient Ping app. From that point, the assigned care manager starts receiving “pings,” which are real time updates alerting the care manager about the MVP patient’s hospital utilization (IP, OBS, ED). The MVP care manager checks on the patient, communicates with providers and helps coordinate care and the transition to home.

**Initial Assessment and Customized Plan.** Shortly after the program start date, each MVP care manager calls patients assigned to her/him to conduct a full assessment. The case manager continues to try to reach the patient, and there is no limit for the number of attempted phone calls over a period of time. The assessment contains review of medications, upcoming appointments, social determinants of health (living arrangements, financial), and a PHQ9 survey. The care manager assesses a patient’s motivation to change, provides education, solicits questions about health, and how the patient wants to be contacted. The care manager uses the assessment to create a customized plan for each patient.

**MVP program features:** Care managers are alerted via Patient Pings when a patient is admitted to hospital or has an ED encounter.

- If a patient is admitted to a hospital, the care manager consults the inpatient case manager and calls the patient if needed
- During monthly huddles, care management reviews charts of patients who had an acute care encounter during the past 30 days.
- In general, if a patient had 0 hospital stays in the previous month, care managers do not make any calls.
- There are no home visits.

- Face-to-face visits may take place if the patient is admitted to a facility at a close proximity to the care manager.

The relationship between a patient and a care manager varies. Care managers strive to identify MVP drivers and resources needed (clinical, financial, social), coordinate medical care and draw on resources from community programs. Community resource referrals depend on the county and availability (e.g., Mecklenburg county has more resources for transportation, food pantry, access to specialists than rural counties). The goal is to engage the patient, develop trusting relationships, offer recommendations tailored to patient, help the patient avoiding unnecessary medical utilization, and over time help the patient achieve stability.

### **5.3. Usual Care**

Patient's post-discharge usual care depends on the inpatient care management assessment at last hospital admission. Patients can be discharged to home and receive no further care, or home with home health, or to a skilled nursing facility (SNF) or another type of Continuing Care facility. Patients can be referred to AIM, hospice, and Community Care Partners by the inpatient care manager. Patient can be referred to Ambulatory Care Management for care management also via telehealth, by a PCP or the Transitions Clinic.

### **5.4. Patient Graduation from the MVP program**

Participation in the MVP program ends if the care manager stops monitoring the patient's health and stops reaching out to the patient. Reasons include:

- a) Patient died
- b) Patient relocated
- c) Patient was incarcerated

The below reasons do not result in ending the MVP participation. Instead, the MVP care manager continues to quietly monitor the patient's health and coordinate services if needed but does not reach out directly to the patient.

- a) Patient no longer wishes to participate
- b) Patient enrolled in palliative/hospice care while enrolled in the MVP program
- d) Patient moved to nursing home or assisted living while enrolled in the MVP program

### **5.5. Continuation of the Intervention**

Patients enrolled in the MVP program may continue participating after the study period has ended.

## 6. DATA COLLECTION AND REPORTING

Data will be obtained from several sources:

- Electronic medical record and billing datamarts
  - i. Patient demographics and health characteristics
  - ii. Medical care utilization: hospital IP and OBS, ED
  - iii. Social determinants of health in the hospital discharge questionnaire
  - iv. Charges
  - v. Paid amount for the subset of Medicare patients (Part A and B)
  - vi. Mortality
- HealtheCare
  - i. Care Management assessment
- PatientPing (third party care management vendor)
  - i. non-AH hospital IP and OBS
  - ii. non-AH ED utilization

Data will be retrieved by an application specialist on the research team. Data will be retrieved retrospective to a patient's completion of the intervention or usual care arm of the study.

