### 1.3. Secondary Objectives

The Secondary Objectives are to

(1) evaluate the effect(s) of participation in the MVP program on:

- 6-month inpatient hospital utilization
- 6-month and 12-month Combined IP and OBS hospital stays at Atrium Health facilities
- 6-month and 12-month Combined IP and OBS hospital stays at AH and other facilities
- 6-month and 12-month IP hospital stays that are readmission eligible (using CMS criteria)
- 6-month and 12-month 30-day readmission rate among patients who had at least one encounter during the time frame
- 6-month and 12-month ED visit rate
- 6-month and 12-month Mortality rate
- 6-month and 12-month Hospital bed days (length of stay, IP)
- 6-month and 12-month Hospital charges

(2) assess variability in MVP program treatment effects associated with predefined patient and program factors, including:

- insurance status
- age, gender, race and ethnicity
- English as second language
- type of care management program (e.g., ACM, etc.)
- community characteristics
- clinical characteristics (e.g., CCI)

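### Mortality has no stated arm-independent source, so deaths outside Atrium Health hospitals could be recorded more fully in the MVP arm and bias the mortality odds ratio against the program

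*Combined protocol and SAP*

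**What the plan says.** Section 1.3 lists "6-month and 12-month Mortality rate" among the secondary objectives, and section 5.1.2 lists mortality among the outcomes cumulated over 6 and 12 months. Section 6.2 reports binary outcomes as odds ratios, with a Wald test at the 0.05 level.

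Section 6 places mortality as the last item under "Electronic medical record and billing datamarts". The one outside feed, PatientPing, is listed for "non-AH hospital IP and OBS" and for non-AH emergency visits, not for deaths. No death index, vital-records linkage or vital-status contact is described. On timing, the section says: "Data will be retrieved retrospective to a patient's completion of the intervention or usual care arm of the study".

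The arms are followed differently by design:

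- **MVP.** Section 5.2 gives each patient an assigned care manager, who receives real-time alerts of hospital use, and monthly team review of recent acute encounters. Section 5.4 names death as a reason for ending participation. It keeps background monitoring in place for patients who withdraw, enter palliative or hospice care, or move to a nursing home or assisted living.
- **Usual care.** Section 4.1 keeps these patients out of MVP. Section 5.3 says: "Patients can be discharged to home and receive no further care". It also allows home health, facility care, and referral to other programs.

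**The concern.** Randomization balances true deaths between the arms. It does not balance how completely deaths are recorded. A death in an AH hospital should reach the AH record in either arm. A death at home, in a nursing facility or in another hospital needs some route into that record, and the protocol describes none. The only systematic post-randomization monitoring it describes is part of the intervention.

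If that monitoring brings more outside deaths into the record, recorded mortality is higher in the MVP arm when true mortality is equal. The trial could then show a false harm signal, or hide a true survival benefit. Intention-to-treat analysis does not correct this, and retrospective retrieval recovers nothing that was never entered.

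Healthy Days at Home, an exploratory outcome in section 5.1.3, could also be distorted. If a death is unknown, the days after it may be counted as days at home.

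**Working it through.** **The plan's own figures.** The plan states no mortality figure. The nearest is the 35% attrition for death and relocation combined in section 6.1: 454 × (1 − 0.35) = 295.1, which reproduces the stated 295 per group. It gives no separate death rate, and it supports a calculation on inpatient encounters, so it neither confirms nor refutes this point.

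**Inputs from the protocol.** 454 randomized per arm (section 6.1); odds ratio and Wald test at 0.05 (section 6.2), taken here as two-sided and without covariates.

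**Inputs assumed, because the protocol gives none.** True 12-month mortality *m* = 20% in both arms; share of deaths outside AH hospitals *o* = 30% or 50%; capture *c* of those outside deaths = 90% in MVP and 80% or 60% in usual care. All deaths in AH hospitals are taken as recorded.

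**Formulas.**

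- Recorded mortality: p = m × [(1 − o) + o × c]
- Odds ratio: OR = [p₁/(1 − p₁)] / [p₀/(1 − p₀)], with MVP as 1 and usual care as 0
- SE of ln OR = √{1/[454 p₁(1 − p₁)] + 1/[454 p₀(1 − p₀)]}
- Rejection probability = Φ(z − 1.96) + Φ(−z − 1.96), with z = ln OR / SE

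**Worked case: o = 50%, capture 90% against 60%.**

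- p₁ = 0.20 × (0.5 + 0.45) = 0.190
- p₀ = 0.20 × (0.5 + 0.30) = 0.160
- OR = (0.190/0.810)/(0.160/0.840) = 1.23
- SE = √(1/69.87 + 1/61.02) = 0.175
- z = 0.208/0.175 = 1.19
- Rejection = Φ(−0.77) + Φ(−3.15) = about 22%

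| Outside share | Capture, MVP / usual care | Recorded, MVP / usual care | OR | Rejection | Extra recorded MVP deaths, 454 × (p₁ − p₀) |
|---|---|---|---|---|---|
| 30% | 90% / 90% | 19.4% / 19.4% | 1.00 | 5.0% | 0 |
| 30% | 90% / 80% | 19.4% / 18.8% | 1.04 | 5.6% | 2.7 |
| 50% | 90% / 80% | 19.0% / 18.0% | 1.07 | 6.7% | 4.5 |
| 30% | 90% / 60% | 19.4% / 17.6% | 1.13 | 10.7% | 8.2 |
| 50% | 90% / 60% | 19.0% / 16.0% | 1.23 | 22% | 13.6 |

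**Sensitivity to the death rate.** With *m* from 10% to 30% and the same formulas, the 10-point gap gives OR 1.04 to 1.08 and rejection of 5% to 8%. The 30-point gap gives OR 1.11 to 1.26 and rejection of 8% to 34%.

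**Masking of benefit.** If true mortality were 17% in MVP and 20% in usual care, the worked case would record 0.17 × 0.95 = 16.2% against 0.20 × 0.80 = 16.0%. The true OR of (0.17/0.83)/(0.20/0.80) = 0.82 would appear as about 1.01.

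**Primary outcome.** Section 6.2 includes all eligible patients and states no offset for time alive. A patient's encounter count is then the same whether or not a later death is known.

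**The case against.** The strongest reply is that the difference in contact is smaller than it looks. A reader might infer from section 5.2, which says that "there is no limit for the number of attempted phone calls over a period of time", that MVP patients are phoned throughout the year and their deaths found that way. The protocol does not support this. That sentence concerns the initial assessment. The same section says that, in general, "if a patient had 0 hospital stays in the previous month, care managers do not make any calls". The monthly reviews cover only patients with an acute encounter in the past 30 days, and there are no home visits. Patients who withdraw, enter hospice or move to a nursing home are monitored but not contacted directly. Many deaths at home or in a facility would fall where calls have stopped.

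A reader might also infer that MVP staff must establish whether a patient has died. Section 5.4 says only: "Participation in the MVP program ends if the care manager stops monitoring the patient's health and stops reaching out to the patient". Death is listed as one reason. No duty to ascertain it is stated, and no route from the care manager to the analysed death field.

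Two further points narrow the gap. Some usual-care patients are referred to ambulatory care management, advanced illness management, hospice or Community Care Partners. And the AH record may already receive outside death data; Medicare claims, under the same source heading, might carry death dates for that subgroup.

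All of this stands, and it limits how large the bias is likely to be. It does not close the gap. Alerts and continued monitoring remain specific to MVP, and the protocol names no source that would record deaths equally in both arms.

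**Conclusion.** The point holds as an open risk, not as a demonstrated bias. Mortality is a tested secondary outcome whose listed source is not shown to be independent of arm, and follow-up differs by arm. If capture differs in the expected direction, the odds ratio is biased against MVP.

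The size cannot be found from the documents. Under the assumptions above, with 20% mortality, a 10-point gap is close to harmless (OR 1.04 to 1.07, rejection 6% to 7% against a nominal 5%). A 30-point gap is not (OR 1.13 to 1.23, rejection 11% to 22%), although even its worst case fails to reject about 78% of the time.

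A reader might go further and conclude that missed deaths bias the primary result, because patients who died count as alive with no admissions. The documents do not support that: admissions before death still count, and the stated model does not use death status. It would matter only if the analysis added an offset for time alive or dropped patients known to have died, neither of which section 6.2 describes. Healthy Days at Home could be affected, but it is exploratory.

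**What to change.** In section 6, replace the mortality entry with a single source applied identically to every randomized patient, without reference to arm:

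- After day 365, link the full randomization list once to state or national death records. Alternatively, confirm in writing that the record's death field is already linked in this way for both arms; a clarifying sentence would then be enough.
- Use that vital status and death date for 6-month and 12-month mortality and for Healthy Days at Home.
- Do not count deaths known only through MVP staff contact.

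With equal capture in both arms, the odds ratio under no true effect returns to 1.00 and the rejection rate to 5%.

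Restricting the outcome to deaths in AH hospitals would not be a sound substitute. It would make mortality depend on being admitted to AH, which the program aims to reduce, so recorded MVP mortality could fall without any survival gain.

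The cost is one batch linkage of about 908 identifiers (2 × 454): a small fee, a data request, and some delay until death records are complete. Randomization, the intervention and the primary outcome are unchanged.

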### 4. SUBJECT SELECTION

#### 4.1. Subjects Accrual and Randomization

1. The list of patients meeting the inclusion criteria will be pulled from AH electronic data warehouse (EDW).
2. Based on chart review, patients not eligible for the MVP program due to exclusion criteria will be removed from the list. Programmatic subgroups will be identified among eligible patients
  - (1) Ambulatory Care Management (ACM) and Advanced Illness Program (AIM)
  - (2) Community Care Partners (CCP) and Community Care of NC (CCNC)
  - (3) Community Care Bridge (CCB)
3. Patients remaining on the list will be randomized 1:1 to Usual Care or MVP referral using stratification to maintain balance across defined programmatic subgroups.
4. The Care Management team will monitor and reach out to patients identified for enrollment in the MVP program during the study period. Patients assigned to usual care will not be enrolled into the MVP program.

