## 4.3. Evaluable Population

Patients included in the evaluable population for this project, will have their data inform the final outcomes assessment. All patients who meet the inclusion and exclusion criteria in both groups will be assessed for the primary outcome (intent to treat).

AH Care Management will enroll patients assigned to the 2020 MVP program cohort on a predetermined date, flagging the MVP program participants as “active” in the care management’s data application (PatientPing).

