### 5.1.2. Secondary Outcome Variables

- The number of IP hospital encounters over a 6-month period.

All secondary outcome variables listed below are cumulative over 6-month and 12-month periods.

- Combined number of IP and OBS hospital encounters at AH hospitals
- Combined number of IP and OBS hospital encounters at both AH + non-AH hospitals
- Among patients with at least 1 encounter during the study period, 30-day all-cause non-elective inpatient readmission rate to any AH hospital
- Among patients with at least 1 encounter during the study period, 30-day all-cause non-elective inpatient readmission rate to the same AH hospital as the index encounter
- Emergency Department encounters
- Mortality
- Hospital bed days (IP)
  - This is the total length of stay (LOS) in days (discharge date – admission date) for acute care inpatient utilization.
- Cost of Care - Hospital charges
  - Total accrued hospital billed charges for inpatient encounter at Atrium Health primary enterprise acute care facilities.

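### Nothing in the plan secures equal capture of non-AH hospital and ED use in the two arms: its only source is PatientPing, and the only entry step described there is for MVP patients

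*Combined protocol and SAP*

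**What the plan says.** Section 6 lists the data sources. AH utilization comes from the medical record and billing datamarts. Under "PatientPing (third party care management vendor" it lists "i. non-AH hospital IP and OBS" and "ii. non-AH ED utilization". No other source is named for these outside encounters. Section 6 also says that data will be pulled retrospectively once a patient has completed either arm.

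PatientPing also appears in four other places, each time in connection with MVP patients:

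- Section 4.3: "AH Care Management will enroll patients assigned to the 2020 MVP program cohort on a predetermined date". The same sentence has those patients marked active in the application.
- Section 5.1.4: the treatment identifier equals 1 only for patients who are both assigned to MVP and flagged active.
- Section 5.2, program start point: the active flag marks the start. "From that point, the assigned care manager starts receiving" alerts on IP, OBS and ED use.
- Section 6.3: the MVP cohort is enrolled at one time and flagged active.

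Section 4.1 adds: "Patients assigned to usual care will not be enrolled into the MVP program". No section describes an equivalent PatientPing step for usual care.

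The outside encounters feed a secondary outcome in section 5.1.2, "Combined number of IP and OBS hospital encounters at both AH + non-AH hospitals", at 6 and 12 months. The same section lists ED encounters without saying whether they are limited to AH. Section 6.2 plans a regression with a Wald test at 0.05 for primary and secondary outcomes.

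**The concern.** A tested outcome draws on a tool that is part of the intervention, and the only documented way into that tool depends on the arm. If being active affects which outside encounters can be retrieved, more of them will be counted for MVP patients than for usual-care patients, even when true use is equal. Neither covariate adjustment nor more patients would remove that error.

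The outcome matters more than its secondary rank suggests. The primary outcome (section 5.1.1) counts admissions to AH acute care hospitals only. The AH + non-AH count is the one listed hospital-stay count that expressly includes outside facilities, so it is the direct check that a fall in AH admissions is not a shift to other hospitals. Unequal capture could hide a real benefit on that check or suggest a shift that did not happen.

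ED encounters are exposed in the same way if non-AH visits are counted. Healthy Days at Home (exploratory, section 5.1.3) would be exposed if outside stays enter its calculation.

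**Working it through.** **The plan's own figure.** The documents give no figure for PatientPing coverage or for the non-AH share of encounters. The one related calculation, in section 6.1, reproduces: a 10.4-point difference, SD 0.45, two-sided 0.05 and 80% power give 294 per group by the normal approximation and 295 by the t test, against 295 stated. It does not depend on PatientPing.

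**Model for the illustration.** Let s be the true share of stays at non-AH hospitals, taken as equal in the two arms. Let cM and cC be the fractions of those outside stays captured in the MVP and usual-care arms. AH stays are taken as fully captured in both. Then

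observed ratio = true ratio × [(1 − s) + s·cM] / [(1 − s) + s·cC].

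If cM = cC, the factor is 1. If cM > cC, it exceeds 1, so the error runs against MVP. All values of s, cM and cC below are assumptions.

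**True null (true ratio 1):**

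| s | cM = 1, cC = 0.5 | cM = 1, cC = 0 | cM = 0.8, cC = 0.4 |
|---|---|---|---|
| 5% | 1/0.975 = 1.03 | 1/0.95 = 1.05 | 0.99/0.97 = 1.02 |
| 10% | 1/0.95 = 1.05 | 1/0.90 = 1.11 | 0.98/0.94 = 1.04 |
| 20% | 1/0.90 = 1.11 | 1/0.80 = 1.25 | 0.96/0.88 = 1.09 |

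The last column keeps the same two-to-one relative capture as the first but makes MVP capture incomplete. The bias is smaller at every share.

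**With a true benefit.** The planning drops in section 6.1 (54% and 43.6%) leave 46% and 56.4% of baseline IP encounters, a ratio of 0.46/0.564 = 0.816. Borrowing that ratio for the AH + non-AH outcome, with cM = 1:

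- s = 5%, 10%, 20% and cC = 0.5: observed 0.84, 0.86, 0.91.
- s = 5%, 10%, 20% and cC = 0: observed 0.86, 0.91, 1.02.

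The ratio of 0.816 is an 18.4% reduction, whereas section 6.1 quotes 21.3%. Using 1 − 0.213 = 0.787 instead, the most extreme case becomes 0.787 × 1.25 = 0.98. Either way, that case removes nearly all or all of the planned benefit.

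**The case against.** The strongest reply is that the documents describe the active flag as what starts alerts to the care manager. They do not describe it as a filter on which encounters the vendor holds. Section 6 lists PatientPing as a study source with no restriction by arm, and its sentence on retrospective retrieval covers both arms. Section 5.3 allows usual-care patients to be referred to care management groups, and whether those groups follow them in PatientPing is not stated. MVP capture may also be incomplete: section 5.4 ends monitoring for patients who relocate or are incarcerated.

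All of this stands. A reader might infer that PatientPing holds nothing on usual-care patients, or that ascertainment is documented to differ by arm. The documents support neither, and the zero-capture column is an outer bound, not an expected value.

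What the reply does not supply is any statement that outside encounters are captured alike. The retrieval sentence says when data are pulled, not whether the vendor will hold usual-care records to pull. If the vendor needs patients on a roster before it records their encounters, omission at the start may not be recoverable at the end. That makes this more than a missing detail.

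**Conclusion.** The point holds as a well-grounded risk: outside encounters come from one source, the only entry step described for it covers one arm, and no provision secures equal capture. The direction is clear if capture is less complete in usual care: the AH + non-AH IP/OBS comparison moves against MVP, and so does the ED comparison if it counts non-AH visits.

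The size is unknown. The ranges of 1.03 to 1.11 (half capture in usual care) and 1.05 to 1.25 (none) for a true null rest on an assumed non-AH share of 5% to 20%, equal in both arms, and on full MVP capture. The observed ratios under a true benefit also borrow a planning ratio for IP encounters and apply it to a broader outcome.

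It would be wrong to extend the point to the primary result. The primary outcome, its 6-month version, IP/OBS at AH hospitals, readmissions to AH hospitals and AH charges do not need PatientPing. The point should be settled before the comparison is relied on, but it does not threaten the main conclusion.

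**What to change.** In section 6, require that all randomised patients in both arms be placed on the same PatientPing roster from the same date, with no alerts sent for usual-care patients. In section 5.1.2, state whether ED encounters are limited to AH facilities. If both arms are already covered, a sentence saying so is enough.

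If the vendor cannot do this, restrict the between-arm IP/OBS and ED tests to AH facilities, and report AH + non-AH results descriptively with a note on possible unequal capture.

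Medicare claims are an alternative only if encounter-level data can be obtained. Section 6 lists Part A and B paid amounts for a subset of patients, not encounters, so claims should not be assumed to be an available source, and they would cover that subset only.

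The cost is a roster upload that depends on vendor and data-sharing arrangements the documents do not describe. Under the fallback, one secondary outcome loses its formal test, and ED is tested for AH visits only.
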